2.3 Benefit/Risk Assessment

Participants who need to have third molar extraction will be solicited to participate in this study. Participants who consent to participate may benefit by receiving a medical exam, dental radiographs and no-cost surgical procedures for teeth extraction. Furthermore, post-surgical participants will be provided continuous nursing care for approximately 24 hours after surgery. Potential risks of the surgical procedure include pain, dry socket, infection, swelling, bleeding, trismus, and lip or tongue numbness. Potential risks related to local anesthesia and mild sedation include paresthesia and drowsiness. Participants who experience a treatment failure can have the option of taking a standard rescue medication commonly used for post-operative pain relief. Potential study medication benefit will be relief of postsurgical pain, which is highly

Version 4.0 / 13 Mar 2023

Page 19 of 67

prevalent following extraction of wisdom teeth. Potential risks of a single dose of OTC study medication are low and described in the Drug Facts Label.

During the study, participants will be closely monitored for evidence of adverse events. Weighing between the potential risks associated with the study, and given the ability to mitigate risks through close monitoring and routine peri-operative care, this study is considered clinically and ethically acceptable.

More detailed information about the known and expected benefits and risks and reasonably expected adverse events may be found in the naproxen sodium Investigator's Brochure and Aleve® Drug Facts Label.

Caffeine has been proven to act as an analgesic adjuvant, providing up to 40% more relief than analgesics alone (Laska, Sunshine et al. 1984). While the analgesia-enhancing effect of caffeine has not been extensively studied with naproxen sodium, a preliminary study (Fricke 1994) showed a positive effect analogous to the results of studies with ibuprofen, another member of the aryl propionic acetic acid family of NSAIDs (Derry, Wiffen et al. 2015). The results of a recently completed dose ranging study with the proposed FDC also showed the beneficial effect of caffeine in enhancing the analgesic effect of naproxen sodium.

In regards to safety, caffeine is included in the monographs for stimulant OTC drug products (21 CFR 340) and for internal analgesic, antipyretic, and anti-rheumatic OTC drug products (21 CFR part 343) as analgesic adjuvant. Although it is generally accepted that 300 mg to 400 mg of caffeine daily may be safely taken by the general population (McGuire 2014), several potentially vulnerable populations have been identified. After a review of available data, Health Canada recommended that women of reproductive age restrict caffeine intake to no more than 300 mg daily, and that children up to 12 years restrict intake to no more than 2.5 mg per kilogram of bodyweight. During pregnancy, the American College of Obstetrics and Gynecology has recommended no more than 200 mg caffeine intake daily (ACOG 2010). Finally, consumers (particularly children) on anticonvulsants or sympathomimetics, as well as consumers with known cardiovascular disease should probably limit caffeine intake.

Risks to vulnerable populations identified above will be addressed through labeling. For example, the proposed label will restrict the product to the same population as the current Aleve® product, which is not indicated for children younger than 12 years old and instructs women to avoid taking NSAIDs around 20 weeks or later in pregnancy. Similarly, the proposed label instructs consumers on any prescription drugs or with any concurrent disease (which includes cardiovascular conditions and seizure disorders) also to consult a physician before use. Finally, the proposed label will include all the necessary instructions for safe and effective use including contraindications, applicable warnings and precautions, and undesirable effects. No further risk-minimization measures are considered necessary for this new product, and its benefit-risk balance is expected to be positive.

Page 20 of 67

3. Objectives and Endpoints

Objectives	Endpoints	
Primary		
To compare a single oral dose of the FDC relative to naproxen sodium 220mg, Caffeine 100 mg and placebo	Sum of Pain Intensity Difference over 8 hours (SPID 0-8)	

Ob	jectives	Endpoints		
Sec	condary			
•	To compare a single oral dose of the FDC relative to naproxen sodium 220mg, caffeine 100 mg and placebo. The assessments are made in terms of:	 Sum of pain intensity differences from 0 to 2, 4 6, 12 and 24 hours post-dose (SPID0-2, SPID0-4, SPID0-6, SPID6-12, SPID0-12, SPID12-16, SPID16-20, SPID12-24, SPID16-24, SPID0-24 		
•	 Pain intensity differences Measures of pain relief Duration of analgesic efficacy Onset of pain relief as determined by the time of perceptible relief Onset of pain relief as determined by the time to meaningful relief Overall relief from pain based on measures of pain intensity and pain relief Global assessment of the investigational product To assess the safety and tolerability of the investigational product in terms of adverse events (AEs) and clinical parameters 	 Total pain relief from 0 to 2, 4, 6, 8, 12 and 24 hours post-doseTOTPAR0-2, TOTPAR0-4, TOTPAR0-6, TOTPAR6-12, TOTPAR0-8 TOTPAR0-12, TOTPAR12-16, TOTPAR16-20, TOTPAR12-24, TOTPAR16-24, and TOTPAR0-24) Time to first use of rescue medication The cumulative proportion of participants taking rescue medication over the 24 hour period. Time to first perceptible relief measured by a stopwatch, time to meaningful relief measured by a stopwatch, and time to first perceptible relief confirmed by meaningful relief defined as the time to perceptible pain relief (the first stopwatch time) for those participants who had meaningful pain relief (the second stopwatch time) 		
		 Pain Intensity Difference (PID) and Pain Relief scores at 0.5, 1, 1.5, 2, 3, 4, 5, 6, 7, 8, 9, 10, 11, 12, 14, (16, 18, 20 if awake), 22 and 24 hours post-dose Peak PID and peak pain relief Time and cumulative proportion of achieving complete pain relief Cumulative percent of participants with 'at least a 2-point PID' over time Global Assessment of the investigational product Collect AE and clinical paramaeters 		

Page 21 of 67

4. Study Design

4.1 Overall Design

Design Overview

This is a single center, randomized, double-blind, parallel, placebo-controlled study in participants experiencing moderate to severe postoperative dental pain. The study will consist of a Prescreening telephone call, a Screening Visit, a one day Treatment Period and a Post-Operative phone call or visit. Eligible participants who have undergone surgical extraction of three or four third molars, 2 of which were mandibular partial or full bony impacted third molars will be kept in-house and evaluated for efficacy and safety at the study site through completion of all trial procedures.

Qualified participants will then be randomized into one of five treatments. Approximately 750 participants will be screened prior to surgery. Approximately 540 will have surgery and approximately 528 will be randomized to a specific treatment.

Screening Phase

Eligible participants will be screened and selected up to 28 days prior to oral surgery and dosing with investigational product (study intervention).

Treatment Phase

Following selection, qualified participants will enter the Treatment Phase and be scheduled for their surgical teeth extractions. After completion of the surgical teeth extractions, participants will remain at the study site for observation. Participants with appropriate pain requirement will be randomized into one of five (5) treatment groups receiving study intervention. Participants will rate their pain severity and pain relief over the next 24 hours. Onset of analgesia will be measured using a two stopwatch approach. The first stopwatch will be used to capture the time when any pain relief is first perceived. The second stopwatch will be used to capture the time when pain relief becomes meaningful to the participant. After completion of all trial procedures, participants will be discharged from the study site.

All participants are required to remain at the study center and complete all relevant assessments regardless of rescue.

Follow-Up Phase

Participants will be evaluated at a post-operative visit/call approximately 2-5 days after discharge for follow up for any adverse events or medications not known at the time of treatment.

The duration of each participant's participation will be approximately 37 days. For an overview on the study design and study procedures (see Figure 1).

Page 22 of 67

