 Onset of pain relief as determined by the time to meaningful relief 	Time to first use of rescue medication		
 Overall relief from pain based on measures of pain intensity and pain relief 	The cumulative proportion of participants taking rescue medication over the 24 hour period.		
O Global assessment of the investigational product To assess the safety and tolerability of the investigational product in terms of adverse events (AEs) and clinical parameters	Time to first perceptible relief measured by a stopwatch, time to meaningful relief measured by a stopwatch, and time to first perceptible relief confirmed by meaningful relief defined as the time to perceptible pain relief (the first stopwatch time) for those participants who had meaningful pain relief (the second stopwatch time)		
	• Pain Intensity Difference (PID) and Pain Relief scores at 0.5, 1, 1.5, 2, 3, 4, 5, 6, 7, 8, 9, 10, 11, 12, 14, (16, 18, 20 if awake), 22 and 24 hours post-dose		
	Peak PID and peak pain relief		
	Cumulative percent of participants with 'at least a 2-point PID' over time		
	Global assessment of the investigational product		
	Collect AE and clinical paramaeters		

Overall Design:

This is a single center, randomized, double-blind, parallel, placebo-controlled study in participants experiencing moderate to severe postoperative dental pain. The study will consist

Version 4.0 / 13 Mar 2023

Page 14 of 67

of a Prescreening telephone call, a Screening Visit, a one day Treatment Period and a Post-Operative phone call or visit. Eligible participants who have undergone surgical extraction of three or four third molars, two of which must be mandibular partial or full bony impacted, will be randomized into one of five treatment groups and kept in-house and evaluated for efficacy and safety at the study site through completion of all trial procedures.

Disclosure Statement: This is a parallel group treatment study with 5 arms that is participant and investigator blinded.

Intervention Model: Parallel Primary Purpose: Treatment

Number of Arms: 5
Masking: No masking
Number of Participants:

Approximately 750 participants will be screened to achieve 540 randomly assigned to study intervention and 528 evaluable participants for an estimated total of 144 evaluable participants per active intervention group with 48 participants in the caffeine 100 mg arm and 48 participants for placebo (total of 5 groups).

Intervention Groups and Duration:

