9.1 Statistical Hypotheses

The primary efficacy endpoint is the sum of change in pain intensity from 0 to 8 hours (SPID₀₋₈). The treatment comparisons will be made in the following sequential order for SPID₀₋₈ (each at 0.05 level of significance) in order to protect overall type 1 error at 0.05:

- Naproxen sodium/caffeine 220/65 mg versus Naproxen sodium 220 mg
- Naproxen sodium/caffeine 440/130 mg versus Naproxen sodium 220 mg
- Naproxen sodium/caffeine 220/65 mg versus Naproxen sodium/caffeine 440/130 mg

Once a comparison is statistically non-significant, the subsequent comparisons will be technically ineligible to be declared significant. However, all pairwise comparisons will be presented to provide a complete picture.

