9.2 Sample Size Determination

Assuming that the treatment difference between the combo and naproxen alone of 6.5 and common standard deviation of 16.9 with respect to SPID₀₋₈, a total of approximately 528 subjects (144 subjects per active treatment arm and 48 in the caffeine and placebo using a 3:3:3:1:1 ratio) are required to achieve 90% of power with the type I error of 0.05, a total of approximately 556 subjects will be randomized into the study if a drop-out rate of 5% is assumed.

Page 44 of 67

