9.4.1 Efficacy Analyses

For each post-dose time point, Pain Intensity Differences (PID) will be derived by subtracting the pain intensity at the post-dose time point from the baseline intensity score (baseline score – post-baseline score). A positive difference is indicative of improvement. Time-weighted Sum of Pain Intensity Differences (SPIDs) will be calculated for 2, 4, 6, 8, 12, 16, 20 and 24 hours by multiplying the PID score at each post-dose time point by the duration (in hours)

Page 45 of 67

since the preceding time point and then summing these values over 0.5, 1, 1.5, 2, 3, 4, 5, 6, 7, 8, 9, 10, 11, 12, 14, (16, 18, 20 if awake), 22 and 24 hours, respectively.

Similarly, Total Pain Relief Scores (TOTPARs), will be calculated by multiplying the pain relief score at each post-dose time point by the duration (in hours) since the preceding time point and then summing these values.

In all analyses for participants who take rescue medication, all pain intensity scores after intake of rescue medication will be imputed by the worse of the baseline or the score assessed immediately before taking rescue medication. All pain relief after intake of rescue medication will be imputed by "no relief" (0).

Endpoint	Statistical Analysis Methods
Primary	The primary efficacy analyses population will be based on the ITT population.
	Sum of Pain Intensity Difference over 8 hours: SPID ₀₋₈ be analyzed using an analysis of covariance model (ANCOVA) with treatment as fixed effect and baseline pain intensity score as the covariate. A 95% of confidence interval (CI) for the treatment differences and pairwise p-values will be calculated based on the above mentioned model.
Secondary	Total Pain Relief over 8 hours: TOTPAR ₀₋₈ will be analyzed similarly as for the primary endpoint.
	Time to first use of rescue medication. If a participant did not take the rescue medication during the treatment period, (s)he will be censored at the time of last assessment. Time to first use of rescue medication will be estimated and plotted using Kaplan-Meier method and analyzed using log-rank test.

Page 46 of 67

Secondary

The SPID0-2, 0-4, 0-6, 6-12, 0-12, 12-16, 16-20, 12-24, 16-24 and 0-24 will be analyzed using the same methodology as for SPID₀₋₈.

TOTPAR0-2, 0-4, 0-6, 6-12, 0-8, 0-12, 12-16, 16-20, 12-24, 16-24 and 0-24 will be analyzed using the same methodology as for SPID₀₋₈.

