2.3 Determination of Sample Size

Assuming that the treatment difference between the combo and naproxen alone of 6.5 and common standard deviation of 16.9 with respect to SPID0-8, a total of approximately 528 subjects (144 subjects per active treatment arm and 48 in the caffeine and placebo using a 3:3:3:1:1 ratio) are required to

achieve 90% of power with the type I error of 0.05, a total of approximately 556 subjects will be randomized into the study if a drop-out rate of 5% is assumed.

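### The plan gives three conflicting randomised totals (528, 540 and 556); only 556 leaves the required 528 after the stated 5% loss, and it exceeds the number operated

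*Protocol*

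**What the plan says.** Three places in the protocol's current text, two of them repeated in the SAP, give the planned number randomised.

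- **Protocol 4.1 (Overall Design):** "Approximately 540 will have surgery and approximately 528 will be randomized to a specific treatment". SAP 2.2 has the same counts.
- **Protocol 1.1 (Synopsis, Number of Participants):** "540 randomly assigned to study intervention and 528 evaluable participants".
- **Protocol 9.2 (Sample Size Determination):** 528 participants, split 144/144/144/48/48, "are required to achieve 90% of power with the type I error of 0.05"; then "a total of approximately 556 subjects will be randomized into the study if a drop-out rate of 5% is assumed". SAP 2.3 agrees: "a total of approximately 556 subjects will be randomized into the study".

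The design inputs in Protocol 9.2 are: "Assuming that the treatment difference between the combo and naproxen alone of 6.5 and common standard deviation of 16.9" on SPID0-8. Protocol 9.1 tests three comparisons in fixed order, "each at 0.05 level of significance", so the first comparison carries the full alpha.

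**The concern.** The figure 528 serves both as the number needed for analysis and as the number randomised. The figure 540 serves both as the number operated and as the number randomised. The same 12 participants (540 − 528) are lost between surgery and randomisation in Protocol 4.1, but between randomisation and evaluation in the synopsis. Protocol 9.2 uses a third figure, based on a loss rate that neither of the other two sections carries.

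No interim analysis is planned (Protocol 9.5), so the randomised total is the planned end of enrolment and the figure against which a reader would check that recruitment stopped on target. As written, 528, 540 or 556 could each be cited as the target. SAP 7.13 reports no changes from the protocol, and the SAP itself contains both 528 and 556.

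**Working it through.** **Inputs**
- Difference 6.5, SD 16.9, power 90%, alpha 0.05 (Protocol 9.2).
- Allocation 3:3:3:1:1, so each active arm holds 3/11 of the total (Protocol 9.2).
- Drop-out 5% (Protocol 9.2, SAP 2.3).
- Sidedness is not stated in the sample size text. I assume two-sided, in line with the planned 95% intervals in Protocol 9.4.1. The assumption is supported below, because it reproduces the stated arm size.

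**Step 1. Reproduce the plan's own figures.**
Normal approximation: n per arm = 2 × (1.96 + 1.2816)² × (16.9/6.5)² = 2 × 10.507 × 6.76 = 142.1, which rounds up to 143. The noncentral t calculation, with df = 2n − 2 and noncentrality 6.5 / (16.9 × √(2/n)), gives 144 per arm and 90.2% power (90.4% by the normal approximation). A one-sided test would need only 116 per arm, so two-sided is the reading that fits.

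Total: 144 × 11/3 = 528. Inflation: 528 / 0.95 = 555.8, so 556. Protocol 9.2 is therefore internally correct.

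**Step 2. Loss implied by each section.**
- Protocol 9.2 and SAP 2.3: 5%, stated.
- Synopsis: 1 − 528/540 = 12/540 = 2.2%.
- Protocol 4.1 and SAP 2.2: no allowance after randomisation, since 528 is already the number required.

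**Step 3. Apply the stated 5% loss to each total.** Remaining = N × 0.95; per active arm = N × 0.95 × 3/11.

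| Randomised | Remaining | Against 528 | Per active arm | Power (t) | Power (normal) |
|---|---|---|---|---|---|
| 528 | 501.6 | −26.4 | 136.8 | 88.7% | 88.9% |
| 540 | 513.0 | −15.0 | 139.9 | 89.4% | 89.6% |
| 556 | 528.2 | +0.2 | 144.1 | 90.2% | 90.4% |

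Example for 528: 6.5 / (16.9 × √(2/136.8)) = 3.18; 3.18 − 1.96 = 1.22; normal power 88.9%.

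**Step 4. The same totals with nobody lost from the analysis.**
- 528: 144.0 per active arm, 90.2% (t).
- 540: 147.3 per active arm, 90.8% (t).
- 556: 151.6 per active arm, 91.6% (t).

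**Step 5. Which of steps 3 and 4 describes the primary analysis?**
Protocol 5.6 defines a dropout as someone who was randomised and dosed. Protocol 9.3 and SAP 6.1 define the ITT set as everyone randomised and dosed, and make it the primary set. SAP 3.1.1 analyses those who stop early up to their last available time point. A protocol-defined dropout therefore stays in the primary analysis, and step 4 applies to it. Step 3 applies to an analysis that removes the 5%.

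**Step 6. Order of events.**
Protocol 4.1 and 8.1.6 randomise after surgery, once pain qualifies. The number randomised cannot exceed the number operated, so 540 operated is incompatible with 556 randomised. The synopsis total of 540, set beside 540 operated, would leave no run-in failures, although Protocol 5.5 provides for them.

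**The case against.** The strongest reply is that nothing of substance turns on this. Every total is given as approximate. The 5% is a cautious allowance: in the dose-ranging study described in Protocol 4.3, 191 of 193 randomised completed per protocol, a loss of 1.0%. At that rate 540 leaves 534 (90.5% power) and 528 leaves 522.5 (89.9%). Because the ITT set keeps dosed dropouts, the primary comparison may need no inflation at all.

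Most of this stands, and it rules out two stronger readings that a reader might infer.

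- **That only 556 delivers 90% power, or that stopping at 528 leaves the trial underpowered.** The documents do not support this. With 528 dosed, the primary ITT comparison has 144 per arm and about 90% power. Even if 5% were removed, the shortfall from 90% would be 0.6 points (540) or 1.3 points (528).
- **That the plan sanctions stopping at 528 or 540.** No section gives a stopping rule at any of these counts. That a site might stop at one of them is an inference from the conflicting targets.

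The reply does not reconcile the totals. The gap between 528 and 556 is 28 participants, which is the whole 5% allowance, and 556 is a derived figure rather than a rounded one. Nor can approximation turn 540 operated into 556 randomised.

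**Conclusion.** The inconsistency is real and lies in the current text of both documents. Of the three totals, only 556 leaves the required 528 after the stated 5% loss; 540 falls 15 short and 528 about 26 short. The number operated in Protocol 4.1 and SAP 2.2 is too small for 556. What separates the totals is the count remaining after loss, not power.

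The effect on power is small. It is 89.4% (540) or 88.7% (528) if 5% are lost from the analysis, and about 90% or slightly above in the ITT set at either total. These figures assume a two-sided 0.05 test, the plan's difference and SD, and exact 3:3:3:1:1 allocation.

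Two limits apply to the ITT figure. It counts dosed participants, so anyone randomised but not dosed is outside it, as is anyone unblinded in an emergency (Protocol 6.3.2). It also takes no account of any dilution from SPID0-8 values cut short by early drop-out, which the documents give no basis to quantify.

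**What to change.** State one randomised total, one loss assumption and a compatible number operated, identically in the synopsis, Protocol 4.1 and 9.2, and SAP 2.2 and 2.3.

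- **If 556 is the target:** replace 528 and 540 as randomised totals and raise the number operated above 556. For illustration, at the yield implied by Protocol 4.1 (528/540), 556 × 540/528 = 568.6, so about 569 operated.
- **If 528 or 540 is the target:** delete 556 and do one of two things. Either state that the ITT set keeps all dosed participants, so no inflation is needed for about 90% power; or give 88.7% (528) or 89.4% (540), labelled as completer power after 5% loss. Without that label the lower figures would understate the power of the primary ITT analysis.

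The cost is wording in five places. No extra enrolment or design change is needed, and the only price is that a completer power, if quoted, will sit slightly below 90%.

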4.2 Scientific Rationale for Study Design

The study is designed specifically to measure the analgesic effectiveness and capture side effect profiles of naproxen sodium and caffeine FDC compared to the individual active ingredients on acute post-surgical dental pain in healthy participants who could benefit from the administration of an analgesic medication. The molar impaction dental pain model has been widely employed with OTC and prescription pain medications, since it is easily standardized, and the participants are relatively healthy and homogeneous. In addition, there are extensive data substantiating the usefulness of the dental pain model in predicting the relative efficacy of a wide range of analgesic medications by comparing several measures of analgesic efficacy, including onset, peak effect, and duration of analgesic activity (Cooper, 2010, Cooper 1976, Kleinert, 2008).

Time to onset will be measured using a double stopwatch method. The double-stopwatch method for measuring first perceptible relief and meaningful relief was developed using the dental pain model (Desjardins 2002). After ingesting the study medication, the participant is asked to depress a stopwatch button when first perceiving any relief (First Perceptible Relief). If and when this stopwatch is depressed, the participant is then given a second stopwatch and asked to depress the button when the relief is perceived as meaningful (Meaningful Relief). Using this method, onset to First Perceptible and Meaningful Relief can be quantified to the nearest minute. This method has been proven to be sensitive and reliable for measuring analgesic onset (Cooper 2010).

The endpoints and study design are consistent with most recent Guidance by FDA and methods advocated by experts (Cooper 2016 and Singla 2014). Additionally, if a participant does not get sufficient pain relief, then rescue medication approved for treating acute pain (e.g., hydrocodone/acetaminophen) may be requested and will be provided under the supervision of the study site staff.

